7.4.4 Safety Analyses

CRE will liaise with clinical team during delivery of MLHC session if any safety concerns arise

At 3- and 6-month follow-up periods, clinical outcomes detailed above will be assessed by study investigators to determine if there are any concerning safety signals (for example, increased exacerbation rates or health service use, COPD severity scores).

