4.7 Participant Withdrawal Criteria

4.7.1 When and How to Withdraw Participants

Participants are free to withdraw from participation in the clinical trial at any time. An investigator may discontinue or withdraw a participant from the clinical trial for the following reasons:

- Pregnancy;
- If any adverse event (AE), laboratory abnormality, or other medical condition or situation occurs such that continued participation in the clinical trial would not be in the best interest of the participant;
- Disease progression which requires discontinuation of the study intervention;
- If the participant meets an exclusion criterion (either newly developed or not previously recognized) that precludes further study participation

MLHC study

The reason for participant discontinuation or withdrawal from the study will be recorded within the participant's research record, and/or legal health record.

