4.7.2 Follow -up for Withdrawn Participants

If a participant withdraws consent, they can also request the withdrawal of their data and/or biological specimens subject to any research-specific restrictions, if applicable. Once withdrawn from the clinical trial, no further research procedures or evaluations will be performed, or additional research-specific data collected on the participant. Reasonable effort will be made to obtain permission to document the reason for withdrawal.

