7.3 Populations for Analyses

Feasibility outcomes will be assessed for all patients referred to study enrolment Clinical outcomes will be assessed for all patients who complete the MLHC program and provide follow-up information. Essentially a Per-Protocol Analysis format.

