7.4.3 Analysis of the Secondary Endpoint(s)

Clinical endpoints:

Assessed prior to study start, at 3 months (end of MLHC program) and at 6 months (follow-up after program completion). Outcomes will be collected by MLHC CREs using a standardized form in Salesforce, as well as a research assistant based on Epic electronic chart review. For continuous variables, difference in the mean (SD) will be calculated at 3 months and 6 months compared to baseline. For dichotomous variables, difference in proportions at 3 and 6 months compared to baseline will be calculated.

MLHC study

- Healthcare system utilization (number of COPD-related outpatient visits, hospital admissions, ED visits, ICU admissions (at baseline will be over the previous 12 months)
- COPD severity (CAT and mMRC scores, and number of COPD exacerbations)
- Health related quality of life (CAT score)
- COPD medication use (COPD controller medication use, oxygen therapy, oral corticosteroid use, antibiotic use, rescue inhaler use)
- Smoking status (packs per year, quit attempts)
- Vaccination status (routine guidelines recommended vaccines received)
- COPD knowledge (Adapted COPD-Q score)
- Self-efficacy score (Adapted COPD Self-efficacy scale score)
- Self-management score (Partners in Health Scale score)
- Healthcare provider referrals prior to using the program (pulmonary rehab, smoking cessation counseling referrals

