8.2 Recording of Adverse Events

All adverse events occurring during the study period will be recorded. At each contact with the research participant, the research team will seek information on adverse events by specific questioning. Information on all adverse events will be recorded immediately

MLHC study

in the participant's research record and/or legal health record, and transcribed into the adverse event log.

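### The 3- and 6-month safety review in 7.4.4 inherits the completers-only population of 7.3, so admissions, ED visits and exacerbations in participants who stop early fall outside it

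*Protocol*

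**What the plan says.** Protocol 7.3 names two populations. Feasibility uses everyone referred. For the rest, "Clinical outcomes will be assessed for all patients who complete the MLHC program and provide follow-up information", which the section describes as "Essentially a Per-Protocol Analysis format". It defines no safety population.

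Protocol 7.4.4 has two parts. The respiratory educators (CREs) raise concerns with the clinical team during sessions. Then, at 3 and 6 months, "clinical outcomes detailed above will be assessed by study investigators to determine if there are any concerning safety signals", with exacerbation rates, health service use and severity scores as examples. The outcomes meant are those of 7.4.3, which include "Healthcare system utilization (number of COPD-related outpatient visits, hospital admissions, ED visits, ICU admissions" and "COPD severity (CAT and mMRC scores, and number of COPD exacerbations". Death is not on that list.

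Other sections bear on who is left out. Section 4.7.1 lists adverse events among the grounds for withdrawal, and also "Disease progression which requires discontinuation of the study intervention". After withdrawal, 4.7.2 says "no further research procedures or evaluations will be performed, or additional research-specific data collected on the participant". Section 8.2 is broader: "All adverse events occurring during the study period will be recorded". Section 7.4.4 does not refer to that log.

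**The concern.** A safety review restricted to people who finished the program selects on something that harm can change. A participant who deteriorates and stops the sessions is among those in whom a signal would be expected, and the population rule leaves that participant out. The setting makes events plausible, because entry requires at least one exacerbation in the previous 12 months (4.4.1).

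The review has consequences. Section 8.5 takes rising health service use or COPD severity at follow-up to the study team and the REB, with study termination among the possible next steps. There is no control group (3.1), no interim analysis (7.4.6) and no data and safety monitoring board (8.7), so no other planned analysis compares event rates. A completers-only rate could look more reassuring than the rate in everyone who started.

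**Working it through.** **Text check.**

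1. 7.4.4 takes its variables from 7.4.3 and names no population of its own.
2. 7.3 is the only place that gives those variables a population: completers with follow-up.
3. 8.5 is worded consistently with this. It places the outcome assessments after program completion and raises its study-level concerns from the follow-up visits.
4. Two groups are therefore outside the review. Participants who stop sessions but stay in the study can still have 3- and 6-month data, because the schedule in 6.2 sets no completion condition, yet 7.3 excludes them. Participants who withdraw have data up to withdrawal only (4.7.2), and 7.3 excludes those data too. An event that led to the withdrawal would be among them.
5. Death is absent from 7.4.3, so the review does not cover it for completers or for stoppers.

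**Size.** The protocol states no completion rate, event rate or derivation of the 50, so there is no figure to reproduce. The following is an illustration. Assumptions: 50 start; a share c of 60–80% completes and gives follow-up; 6-month admission risk is 10% in completers and p of 10–40% in stoppers, with at most one admission counted per participant.

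- Admissions seen = 50 × c × 0.10
- Admissions outside = 50 × (1 − c) × p
- Share outside = outside / (seen + outside)

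| Completers / stoppers | p | Seen | Outside | All-starter rate | Share outside |
|---|---|---|---|---|---|
| 40 / 10 | 10% | 4 | 1 | 5/50 = 10% | 20% |
| 40 / 10 | 20% | 4 | 2 | 6/50 = 12% | 33% |
| 40 / 10 | 40% | 4 | 4 | 8/50 = 16% | 50% |
| 30 / 20 | 10% | 3 | 2 | 5/50 = 10% | 40% |
| 30 / 20 | 20% | 3 | 4 | 7/50 = 14% | 57% |
| 30 / 20 | 40% | 3 | 8 | 11/50 = 22% | 73% |

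The completers-only review shows 10% in every row. Where the risks are equal, 10% is also the all-starter rate: the rate is unbiased and only the count falls.

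**Precision.** If no events are seen, the exact one-sided 95% upper bound is 1 − 0.05^(1/n): 5.8% for n = 50, 7.2% for n = 40 and 9.5% for n = 30. A clean result in completers alone excludes less.

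**Collection window.** Section 8.1 ends adverse event collection 30 days after the last administration of the intervention. If that is a session at week 12, collection ends at 84 + 30 = 114 days, and earlier for anyone who stops sooner. The schedule in 6.2 nevertheless has an adverse event review at 6 months.

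**The case against.** The strongest reply is that these events are not lost. Adverse event recording (8.2) and 24-hour reporting of serious events to the sponsor (8.3.1) are not limited to completers, and the definition of a serious event in 8.1 covers deaths and hospital stays. An Early Termination Visit assesses adverse events where it can be arranged (4.7.3), CREs escalate concerns during the program (7.4.4, 8.5), and 9.1 allows the trial to be stopped after review of serious, unexpected and related events. All of this stands. A reader might infer that the completers-only review is the sole safeguard, and the protocol does not support that. What remains is that these routes work case by case, and none is brought into the review for increased rates.

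A reader might also infer that 7.3 strips deaths out of the safety conclusion. It does not. Death is not a 7.4.3 outcome for anyone, so the gap lies in what 7.4.4 reviews, not in the population rule.

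Third, the 7.4.4 wording identifies variables, not people, and 7.3 does not mention safety, so the carry-over is a reading of two sections together. That is fair. But 7.3 is the only population given for these outcomes, and a statistical analysis plan that followed the protocol would inherit it.

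Last, the size rests wholly on assumed rates. That also stands. Shares above 40% in the table arise only when stoppers are assumed to carry a higher risk than completers.

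**Conclusion.** The point holds in a limited form. As written, the one aggregate safety review covers completers with follow-up, and admissions, ED visits and exacerbations in those who stop early are outside it, although the protocol itself expects that worsening may lead to stopping. The review covers no deaths at all. Under the stated assumptions 20–73% of admissions fall outside. The understatement of the rate runs from none (equal risk) to 10% shown against 22% in all starters.

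The documents do not support a claim that harms in early stoppers go unmonitored, or that study termination depends on this review alone. It is 8.5, not 7.4.4, that links rising health service use to termination, and 9.1 gives separate grounds. The defect is one of population and data source in the aggregate review. It should be corrected, but it does not mean that safety oversight is absent.

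**What to change.** - **7.3:** state that the restriction to completers with follow-up applies to the effectiveness analysis only. Define a safety population of all participants who start the program, whether or not they complete it or provide follow-up.
- **7.4.4:** run the 3- and 6-month review of admissions, ED visits and exacerbations on that population, with the number started as denominator. Add adverse events, serious adverse events and deaths from the 8.2 log. For participants who withdraw, use the data up to withdrawal, in keeping with 4.7.2.
- **8.1 and 6.2:** reconcile the 30-day collection window with the adverse event review scheduled at 6 months.

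The cost is a few sentences. The log and the 3- and 6-month visits are already planned, and the effectiveness population is unchanged. The limitation is that follow-up will be incomplete for participants who withdraw. The report should say so and give the number of starters followed to 6 months beside the event counts, since a count over all starters can still understate risk when some were observed for less time.

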7.4.5 Baseline Descriptive Statistics

Gender, age in years, education (highest level completed), race/ethnicity, type of smartphone used, smartphone use frequency, baseline clinical outcomes listed above

7.4.6 Planned Interim Analyses

N/A

7.4.7 Sub Group Analyses

N/A

7.4.8 Tabulation of Individual Participant Data

N/A

7.4.9 Exploratory Analyses

N/A

MLHC study

8.0 **SAFETY AND ADVERSE EVENTS**

8.1 Definitions

Adverse Event

An adverse event (AE) is any untoward medical occurrence in a research participant administered an investigational product and which does not necessarily have a causal relationship with this treatment. An adverse event (AE) can therefore be any unfavourable and unintended sign (including an abnormal laboratory finding), symptom, or disease temporally associated with the use of a medicinal (investigational) product, whether or not related to the investigational product.

Serious Adverse Event

A serious adverse event (SAE) is any AE that is:

- Fatal;
- Life-threatening;
- Requires or prolongs hospital stay;
- Results in persistent or significant disability or incapacity;
- A congenital anomaly or birth defect; or
- An important medical event (events that may not be life threatening but are of major clinical significance, such as a drug overdose or seizure that did not result in inpatient hospitalization).

Adverse Event Collection Period

The period during which adverse events must be collected is normally defined as the period from the initiation of any research procedures to the end of the study treatment follow-up. For this clinical trial, the study treatment follow-up is defined as 30 days following the last administration of the study intervention.

Post-study Adverse Event

At the last scheduled visit, the PI and/or QI will instruct each participant to report any subsequent event(s) that the participant believes might reasonably be related to participation in this clinical trial. The PI and/or QI will notify the study sponsor of any death or adverse event occurring at any time after a participant has discontinued or terminated participation that may reasonably be related to this clinical trial. The sponsor will also be notified if the PI and/or QI should become aware of the development of cancer or of a congenital anomaly in a subsequently conceived offspring of a participant that was involved in this clinical trial.

Abnormal Laboratory Values N/A

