14.0 CLI		
17.1	- I UINU NO OUNCE	

MLHC study Version date: 28/05/2024

14.2	CONFLICT OF INTEREST	27
15.0 PU	BLICATION POLICY/DATA SHARING	27
15.1	FUTURE SECONDARY USE OF DATA	45
16.0 RF	FERENCES	27

MLHC study Version date: 28/05/2024

STATEMENT OF COMPLIANCE

This clinical trial will be carried out in accordance with the following:

- International Conference on Harmonisation Good Clinical Practice (ICH GCP)
- Tri-Council Policy Statement 2018 (TCPS 2)
- Personal Health Information Protection Act (PHIPA), 2004; Chapter 3 Schedule A (PHIPA) and applicable regulations
- Institutional and REB policies and procedures

/_/_:	
/ //	May 6 th , 2024
Signature of PI	Date

LIST OF ABBREVIATIONS

Include a list of abbreviations used within the research protocol. A sample list is included below:

AE Adverse Event

CRE Certified Respiratory Educator

COPD Chronic Obstructive Pulmonary Disease

CRF Case report form(s)

DSMB Data Safety & Monitoring Board

GCP Good Clinical Practice

ICF Informed consent form

MLHC My Lung Health Coach

PHI Personal Health Information

PHIPA Personal Health Information Protection Act

PI Principal Investigator

QI Qualified Investigator

SAE Serious Adverse Event

SUSAR Suspected unexpected serious adverse reaction

TCPS 2 Tri-Council Policy Statement

CLINICAL TRIAL SUMMARY

Short Title	MLHC clinical study
Phase	Pilot study
Methodology	Single arm pilot study
Clinical trial Duration	12 months
Participating site(s)	Single site – Women's College Hospital
Objectives	To evaluate the feasibility and effectiveness of MLHC, a COPD self-management and education support program delivered virtually with an electronic patient-record integrated companion app
Number of Participants	50
Study Intervention Reference Therapy/Comparator	The intervention will be enrollment in the MLHC program (a COPD self-management and education support program delivered virtually), and access to the Epic Care Companion MLHC companion app. There will not be a control group for this pilot study.
Duration of Intervention	12 weeks intervention duration, 6 months total follow-up

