5.3 Method for Assigning Participants to Treatment Groups N/A – single arm study

5.4 Administration of Study Intervention

MLHC will be delivered virtually through secure videoconferencing software (Zoom) by CREs as detailed above. All onboarding for the virtual program will be completed by the CREs. Upon study consent, patients will also be oriented to the use of the MLHC Care Companion app by study staff virtually or in-person. They will be shown how to download and login to the Epic Care Companion app, and how to navigate through the MLHC materials. Any tech support needed throughout the study will also be provided by study staff at WCH.

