6.2 Schedule of Events

Procedures	Screening Day -7 to -1	Baseline Visit 1, Day 1	Study Visit 2, 3 months	Study Visit 3, 6 months
Informed consent	X			
Confirming eligibility	X			
MLHC companion app orientation	X			
Demographic information	X			
Health system utilization		Χ	X	X
COPD severity (CAT and mMRC scores)		X	Х	X
Health-related quality of life (CAT score)		X	X	X
Mediation review		X	X	X
Smoking status review		Χ	X	X
Vaccination status review		Χ	X	X
Adapted COPD-Q score (knowledge of COPD)		Χ	X	X
Adapted COPD Self-Efficacy score		Χ	X	X
Partners in Health Scale score (self-management)		Χ	Χ	X
COPD referrals review (rehab, smoking cessation)		X	X	X
Adverse event review and evaluation		X	Х	X
Complete Case Report Forms (CRFs)	X	X	X	X

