8.3 Reporting of Serious Adverse Events

8.3.1 Investigator Reporting: Notifying the Sponsor SAEs will be reported to the sponsor within 24 hours of becoming aware of the event.

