8.5 Safety Management Plan

Participants will be followed bi-weekly by CREs during their participation in the MLHC virtual program. Should any safety concerns arise during this period of the study in relation to COPD severity, exacerbations, or increased healthcare visits, CREs will contact the study team and cases will be discussed on an individual basis. The study team will then liaise with the participant's regular health care team to arrange any necessary follow-up. Following completion of the program, participants will be assessed for clinical outcomes at 3 months and 6 months post-study initiation, at which time safety concerns will also be evaluated, and communicated with the study PI as needed. The study team will then liaise with the participant's regular health care team to arrange any necessary follow-up. As the intervention being delivered represents guideline-based self-management and education support, there is unlikely to be any harm associated with it (this is supported by recent systematic review and meta-analysis data of selfmanagement interventions in COPD). However, though the study is not powered to detect clinical effectiveness, if there are any safety concerns related to study participation at follow-up visits in terms of increased health service use and COPD severity (ED visits, hospitalizations, COPD exacerbations), these will be communicated to the study team, REB and the next appropriate steps will be considered, including but not limited to study termination.

MLHC study

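### The adverse event collection period in Protocol 8.1 appears to end about two months or more before the 6-month visit, where 6.2 schedules an adverse event review

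*Protocol*

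**What the plan says.** Section 8.1 of the Protocol says that adverse events must be collected from the first research procedure to the end of study treatment follow-up. It then fixes that end: "For this clinical trial, the study treatment follow-up is defined as 30 days following the last administration of the study intervention".

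Other parts of the Protocol run to 6 months:

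- The Clinical Trial Summary gives "12 weeks intervention duration, 6 months total follow-up".
- The schedule in 6.2 has a row "Adverse event review and evaluation", marked at baseline, 3 months and 6 months.
- Section 8.2 says "All adverse events occurring during the study period will be recorded" and requires specific questioning about adverse events at each contact. It does not define the study period.
- Section 8.5 describes the 3- and 6-month assessments as the time "at which time safety concerns will also be evaluated". Section 7.4.4 also has the investigators look for safety signals at 6 months.

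Section 8.3.1 sets the reporting duty: "SAEs will be reported to the sponsor within 24 hours of becoming aware of the event". It names no period of its own.

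Section 8.1 also has two post-study rules. At the last scheduled visit, participants are asked to report later events that they think may be related to the trial. Separately, the investigator notifies the sponsor of possibly related deaths or adverse events that occur after a participant has discontinued or ended participation.

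**The concern.** Section 8.1 ties the collection period to the end of the intervention, while the visits and the other safety sections are tied to 6 months of follow-up. With a 12-week intervention and 6 months of follow-up, 30 days does not bridge the two.

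What is at stake is the safety record in the last third or more of follow-up. Take a participant admitted to hospital on day 150 for a reason other than COPD. The admission makes the event serious under 8.1's own definition. It falls outside the period in which 8.1 requires collection, yet the participant will be asked about it at the 6-month visit under 6.2 and 8.2. Staff are not told whether it belongs in the adverse event log, or whether the 24-hour duty in 8.3.1 applies. Different staff could handle the same event differently, and the 6-month adverse event listing would then be hard to interpret.

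**Working it through.** The Protocol gives no end day for the period, so the dates below are derived.

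**Inputs**

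- Intervention: 12 weeks = 84 days (Clinical Trial Summary).
- Sessions: six, ideally one every 2 weeks (5.2).
- Collection after last administration: 30 days (8.1).
- Visits: 3 and 6 months after baseline (6.1, 6.2).
- Assumption: days are counted from baseline as day 0, with 3 months = 13 weeks = 91 days and 6 months = 26 weeks = 182 days.
- Assumption: last administration means the last educator session. Section 5.4, which is headed as administration of the intervention, supports this: "MLHC will be delivered virtually through secure videoconferencing software (Zoom) by CREs as detailed above". So does the 12-week duration in the Summary.

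**Formulas**

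End of period = day of last session + 30. Gap = 182 − end of period. Share = gap / 182.

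| Last session | End of period | Gap | Share of follow-up |
|---|---|---|---|
| Day 70 (sixth fortnightly session, first on day 0: 5 × 14) | 70 + 30 = 100 | 182 − 100 = 82 days | 82/182 = 45% |
| Day 84 (end of week 12) | 84 + 30 = 114 | 182 − 114 = 68 days | 68/182 = 37% |
| Day 91 (3-month visit) | 91 + 30 = 121 | 182 − 121 = 61 days | 61/182 = 34% |

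Placing the 6-month visit anywhere from day 180 to day 183 shifts each gap by −2 to +1 days; the day-84 case then gives 66 to 69 days.

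**The other reading of administration**

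The Summary counts app access as part of the intervention, and 5.2 allows app use after the program ends. If each app use counts as administration, the period ends 30 days after each participant's last use. It then differs between participants and may run past 6 months. Section 8.1 does not say which reading applies.

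**Do the post-study rules fill the gap?**

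- The participant instruction is given at the last scheduled visit, at 6 months, and concerns later events. It does not reach back into the gap.
- The investigator's duty to notify the sponsor begins once a participant has discontinued or ended participation. It does cover someone who left early, but only for possibly related events.
- For a participant still in follow-up between about day 114 and day 182, neither rule applies.

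**What is captured anyway?**

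Exacerbations and COPD-related outpatient visits, emergency visits, admissions and intensive care admissions are 6-month secondary outcomes (3.3), and 7.4.4 and 8.5 review them for safety. The gap therefore concerns adverse event logging and serious event reporting, chiefly for events outside those outcomes.

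**The case against.** The strongest reply is that the sections can all be followed at once. Section 8.1 states when events must be collected; it does not forbid recording later ones. Staff who follow the wider rules in 6.2 and 8.2 break nothing in 8.1, and once they learn of a serious event, 8.3.1 applies without a time limit. The mark at 6 months in 6.2 is also needed on a strict reading of 8.1: events between the 3-month visit (day 91) and day 114 can be picked up at a scheduled review only at 6 months. No planned estimate changes, because 7.4.4 works from the clinical outcomes.

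Much of this stands. A reader might infer that 8.1 flatly contradicts 8.2. The text does not support that, because 8.2 leaves its study period undefined; the misfit with 6.2 is the clearer one. A reader might also infer that no rule in 8.1 covers anyone after day 114. That goes too far, because the notification duty covers possibly related events in participants who have already left. And a reader might infer that late safety events are lost. The COPD events are not.

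What the reply does not remove is the uncertainty. The 30-day rule is written for this trial specifically, under a heading that defines the collection period. If it is only a minimum, the Protocol nowhere says what the actual period is or which section governs. The need to pick up events from days 91 to 114 explains why a 6-month review exists, but not how to treat what that review finds after day 114.

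**Conclusion.** The point holds as a minor inconsistency. On the reading that the Summary and 5.4 favour, the required collection period ends at about day 114 (100 to 121) and leaves about 68 days (61 to 82), or 34% to 45% of a 182-day follow-up, before the last visit. These figures rest on taking the last educator session as the last administration and on 13- and 26-week visit dates. If app use counts instead, there is no fixed gap but also no fixed end, so the sentence needs repair either way.

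The practical consequence is limited to how adverse events outside the COPD outcomes are logged, and how serious ones are reported, for participants still in follow-up. The intervention is low-risk education, the COPD outcomes are retained, and the feasibility and clinical analyses are unaffected.

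**What to change.** In 8.1, replace the 30-day sentence with a fixed period:

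- from the first research procedure to the 6-month visit, regardless of app use;
- for participants who withdraw, to the early termination visit if it is held, and otherwise to the date of withdrawal.

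The second line needs this order because the visit in 4.7.3 follows withdrawal and is arranged only where possible, while 4.7.2 stops further evaluations once a participant has withdrawn.

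Add that this period is the study period meant in 8.2, and that reporting under 8.3.1 applies throughout it. The period then meets the existing post-study rules, which start at the last scheduled visit or on discontinuation.

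Cost: a few sentences in section 8 and no added visit, since the 6-month review is already scheduled. The downside is about two more months (61 to 82 days) per participant in which adverse event logging and 24-hour serious event reporting clearly apply.
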